## **4 Subject Selection and Withdrawal**

### **4.1 Inclusion Criteria**

Participants will include healthy, unmedicated perimenopausal women ages 44-55 either with ( $n=20$ ) or without ( $n=20$ ) current major depression. Thus, only participants capable of giving informed consent will be enrolled. Participants will be compensated upon completion of the study.

#### ***Inclusion Criteria.***

1. Perimenopause Status: We will employ the Stages of Reproductive Aging Workshop (STRAW) criteria to confirm perimenopausal status. The stages are primarily based on the characteristics of the menstrual cycle and secondarily on follicle stimulating hormone (FSH) levels. The anchor for the staging system is the final menstrual period (FMP). We will enroll women who have  $\geq 2$  skipped cycles and an interval of amenorrhea  $\geq 60$  days, consistent with the late menopause transition (stage -1), and who demonstrate an FSH level higher than two SDs above the mean for follicular phase premenopausal women based on UNC Hospitals laboratory levels ( $x= 7$  IU/mL). Because extremes of body weight (BMI  $< 18$  or  $> 30$  kg/m^2) or a history of chronic menstrual cycle irregularity can contribute to inaccurate reproductive staging, these will serve as additional exclusion criteria;
2. MDD Group Eligibility Criterion: current diagnosis of MDD with an onset associated with menstrual cycle irregularity, and no history of psychiatric illness during the 2 years before the onset of the current depressive episode as determined by the Structure Clinical Interview for DSM-IV-TR for Axis I Disorders (SCID);

3. Control Group Eligibility Criterion: absence of any past or present psychiatric disorder as assessed by the SCID.

## 4.2 Exclusion Criteria

. Patients will not be permitted to enter this protocol if they have any of the following:

1. current medication use (i.e., psychotropics, anti-hypertensives, statins, hormonal preparations, or frequent use of anti-inflammatory agents (> 10 times/month)). Women will be allowed to enroll who take medications without known mood effects (e.g. stable thyroid hormone replacement and occasional (< 5 times/month) use of Ambien)\*;
2. pregnant, breastfeeding or trying to conceive;
3. FMP more than 12 months prior to enrollment;
4. history of undiagnosed vaginal bleeding;
5. undiagnosed enlargement of the ovaries;
6. polycystic ovary syndrome;
7. history of breast or ovarian cancer;
8. first degree relative with ovarian cancer;
9. first degree relative with premenopausal or bilateral breast cancer;
10. 2+ first degree relatives with breast cancer (regardless of onset);
11. 3+ relatives with postmenopausal breast cancer;
12. abnormal finding in a provider breast exam and/or mammogram;
13. known carrier of BRCA1 or 2 mutation;
14. endometriosis;
15. blood clots in the legs or lungs;
16. porphyria;
17. diabetes mellitus;
18. malignant melanoma;
19. Hodgkin's disease;
20. recurrent migraine headaches that are preceded by aura;
21. gallbladder or pancreatic disease\*\*;
22. heart or kidney disease\*\*;
23. liver disease;
24. cerebrovascular disease (stroke);
25. first degree relative with history of heart attack or stroke;
26. current cigarette smoking;
27. current suicidal ideation or psychosis;
28. past suicide attempts or psychotic episodes requiring hospitalization;
29. chronic depression (i.e., episode(s) lasting 3+ years);
30. recurrent depression (i.e., more than 1 prior episode, not including episodes with postpartum onset)
31. depressive episode(s) within 2 years of enrollment;
32. self-reported claustrophobia
33. peanut allergy

\*all reported prescription medications will be reviewed and cleared by a study physician prior to a participant's enrollment;

\*\*participants will be given the opportunity to describe these conditions in the online screening survey. Reported conditions that are acute in nature and/or benign will be reviewed by a study physician and exclusions will be decided case-by-case. All chronic conditions will be exclusionary.

## 4.3 Subject Recruitment and Screening

**Methods of recruiting for this study include:**

- Letters
- Flyers
- E-mail announcements

- Facebook advertisements
- Craigslist advertisements

Recruitment materials (e.g., advertisements) will also be placed in university buildings and local businesses, and a university wide email will be used to recruit participants. Advertisements, including the letter, flyer, and email, will instruct participants to call our research lab to complete a phone screen or follow a link to our online eligibility survey. The phone screen and online eligibility survey include same questions (see attached).

#### **Eligibility screening will include:**

- An initial phone or online screening that includes questions about past medical and mental health history to assess potential participants' eligibility based on the criteria listed in sections 4.1 and 4.2.
- Participants will undergo a Clinical and Health Screening process to determine whether they are healthy enough to participate in this study. This screening will include past medical and mental health history and physical exam. During this evaluation, they will be asked questions about past and present psychiatric symptoms. They will also be asked to complete questionnaires about psychiatric symptoms. They may choose not to answer any or all of the questions for any reason.
- Participants will complete a safety questionnaire to determine whether they have any foreign iron or steel metal objects in their bodies, such as a pacemaker, shrapnel, metal plate, or metal debris. If they have any such objects in their bodies, they cannot participate in the MRI session.
- All participants will receive a pregnancy test. No pregnant women will be entered into the study, because the study drugs (estrogen and progesterone) may be associated with birth defects.

### **4.4 Early Withdrawal of Subjects**

#### **4.4.1 When and How to Withdraw Subjects**

Participants with significant clinical or laboratory abnormalities will be discontinued from the study prior to estrogen administration.

Adverse mood symptoms will be monitored by administering the the Hamilton Rating Scale for Depression (HRSD) at each study visit. **If suicidal thoughts or severe mood symptoms are observed at any period in the medication phase, then the suicide item of the HRSD will be administered on consecutive days for three days. Anyone who expresses suicidal thoughts with plans or intent, or who expresses concern about her ability to continue in the study, will be considered to have severe mood symptoms and be discontinued from the protocol.** In the event of the occurrence of severe mood symptoms, the protocol will be terminated. Should this step prove to be unsuccessful, conventional medication will be prescribed as needed. Although we do not anticipate severe adverse reactions, we have arranged for inpatient hospital admission in the Psychiatry Department if symptoms are otherwise unmanageable.

Any patient experiencing clinically significant side effects such as nausea, hypertension, vomiting or extreme fluid retention from the medication will have the dose titrated to achieve relief of the symptoms. If adequate relief cannot be achieved in this manner, drug treatment will be discontinued.

The determination of when and how to withdrawal subjects will be overseen by the study's principal investigator, co-investigators, and research coordinators and will be reported to the UNC Biomedical IRB.

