### 1.1 Background

Despite decades of clinical research, affective disorders continue to affect 20.9 million Americans each year and remain the leading cause of disability worldwide. Unraveling the pathophysiology of affective disorders has been uniquely challenging because depressive syndromes are heterogeneous and have diverse etiologies. Attempts to identify genetic and neural biomarkers that would improve the prediction of susceptibility, course of illness, and treatment response have yielded inconsistent results. One way to solve the problem of etiological diversity and diagnostic heterogeneity is to identify a homogeneous depression subtype with an identified etiology. Reproductive affective disorders (i.e., premenstrual dysphoric disorder, postpartum depression, and perimenopausal depression) represent more homogeneous subtypes, and a clear role for reproductive steroids has been established in these conditions. Thus, we propose to study the pathophysiology of affective dysfunction by examining neural function in women with a specific depression subtype, perimenopausal depression.

Women with perimenopausal depression represent the ideal population in which to study the neural biomarkers of reproductive affective dysfunction because the presumptive etiology—ovarian hormone withdrawal—is objectively measurable and amenable to manipulation. Evidence supporting the role of ovarian hormone withdrawal in the etiology of perimenopausal depression includes the following: perimenopausal women show a temporal association between ovarian hormone withdrawal and the onset of mood symptoms in the late perimenopause; treatment with estrogen reduces mood symptoms; and blinded estradiol withdrawal re-precipitates depression in women with a history of perimenopausal depression (manuscript in preparation). Thus, perimenopausal depression represents a relatively pure phenotype with respect to the presence of hormone sensitive depression. Focusing on a homogeneous etiology will increase the likelihood of identifying meaningful neurobiological markers.

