2. **Estradiol withdrawal is associated with the onset of perimenopausal MDD, and estradiol treatment reduces perimenopausal MDD symptoms compared with placebo**. In a 5-year longitudinal study of 29 women, a 14-fold increase in MDD was observed in the 24 months surrounding menopause. In a larger cross sectional study (n=116), depressive episodes were significantly more likely during the late perimenopause compared with the pre-, early-, and post-menopause. Although estradiol levels are highly variable in regularly cycling women and during the pre- and early perimenopause, the average level of circulating estradiol declines dramatically during the transition from early to late perimenopause, which is accompanied by an increased incidence in MDD. Depressive symptoms significantly decreased following 3 weeks of estradiol treatment in 34 women with perimenopausal MDD compared with baseline and women taking placebo (Figure 1c). Moreover, despite comparable ovarian hormone levels in women with perimenopausal MDD compared with controls, women with a history of perimenopausal MDD (but not those lacking that history) rapidly experience depression recurrence when blindly withdrawn from estradiol. Thus, estradiol withdrawal appears to trigger perimenopausal MDD in susceptible women, and three weeks of treatment with estradiol is sufficient to treat perimenopausal MDD.
3. **Active MDD symptoms and MDD risk are associated with frontostriatal hypoactivity**. Individuals at high risk for MDD show reduced frontostriatal activation during the proposed monetary incentive delay task, and the degree of activation is associated with the severity of self-reported rumination among those at high risk for MDD.
4. **Estradiol levels are associated with increased reward-related neural function during the menstrual cycle in non-depressed women**. Estradiol levels were positively correlated with activation of the dorsolateral and frontopolar cortices, which is consistent with our hypothesis that estradiol supplementation will increase activation in frontal regions.

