
Adverse Events Related to Combined Hormone Replacement and the Results of the Women's Health Initiative (WHI): The WHI study demonstrated that continuous administration of one form of estrogen (conjugated estrogens) in combination with one form of progesterone (medroxyprogesterone acetate) is associated with an increased risk of dementia, heart attacks, stroke, blood clots, and breast cancer. Estradiol, the form of estrogen that we use in this study, is administered as a sole agent (with the exception of one week's combination with progesterone) and, consequently, we do not expect that it will

pose the increased risks observed with the chronic combination of the conjugated estrogens and medroxyprogesterone administered in the WHI study. Indeed, while the estrogen alone arm of the WHI trial was shown to be associated with an increased risk of stroke, no increased risk of either heart disease or breast cancer was observed. Estrogens may precipitate migraine headaches, and depression has also been reported to occur with the use of estrogens. In general, considering the dose and duration of treatment that we propose to use in this protocol, the risk of developing such side effects is negligible.

**Progesterone:** Progesterone and the synthetic progestins are widely prescribed, with indications including dysfunctional uterine bleeding, endometriosis, mastodynia, galactorrhea, and precocious puberty. Side effects reported in women taking progestins may include breakthrough bleeding, edema, change in weight (increase or decrease), cholestatic jaundice, rash (with or without pruritus), depression, easy fatigue and sedation, lack of initiative, and chloasma. Since progestins are often used in women with antecedent menstrual irregularity, it is not clear whether the breakthrough bleeding represents an effect of the medication or refractoriness to treatment. In the large majority of patients, menstruation occurs predictably following withdrawal of progestins and is usually more regular than in spontaneous cycles. In a recent study, an average dose of 1750 mg of oral micronized progesterone was given to 59 women with PMS for a period of three months and was well tolerated by this sample. The side effects reported on progesterone were lightheadedness, fatigue, forgetfulness, and headaches. These were very mild and caused no dropouts.

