**Clinical Assessments**

The Structured Clinical Interview for DSM-IV-TR Axis-I Disorders (SCID) and the Schedule for The SCID1 will be administered at baseline to determine study eligibility. The following standard measures will be administered at baseline, both fMRI sessions, and weekly clinic visits:

- The Positive and Negative Affect Schedule is a 20-item questionnaire that measures both positive affect (PA) and negative affect (NA) and is sensitive to subtle changes in affect over time.
- The Hamilton Rating Scale for Depression (HRSD) is a 21-item researcher-rated standardized scale that assesses depressive symptoms and is widely used as a measure of symptom change over time.
- The Inventory of Depression and Anxiety Symptoms (IDAS) is a 64-item self-report questionnaire that comprehensively assesses anxiety and depression symptoms on 10 subscales. The IDAS has excellent psychometric properties and has been validated for assessing reproductive mood disorders.
- The Mood and Anxiety Symptom Questionnaire - Anhedonic Depression Subscale (MASQ-AD) is a 22-item scale that assesses anhedonia (i.e., loss of interest and low positive affect). MASQ-AD scores have been associated with blunted striatal response to reward in previous studies of patients with depression.
- The Greene Climacteric Scale (GCS) is a 21-item scale that is the gold-standard measure of four domains of climacteric symptoms: vasomotor, somatic, anxiety, and depression.
- The Pittsburgh Sleep Quality Index (PSQI) is a 9-item questionnaire that measures the quality and sleep patterns in older adults. \*This measure will only be administered at the two fMRI sessions.

While the SCID and HAM-D are researcher administered, the other measures will be collected through self-report questionnaires using *Qualtrics* or paper and pencil questionnaires.

Despite the use of exclusion criteria designed to reduce risk to participants, depressive symptoms are monitored closely. Any subject who develops severe depressive symptoms (e.g., suicidal ideation) will be discontinued from the study and offered treatment paid for by the study. If inpatient hospitalization becomes

necessary as a result of the study, UNC Health Care will cover the cost. The following language has been added to the study consent form to reflect this policy:

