### Clinical Assessments

The Structured Clinical Interview for DSM-IV-TR Axis-I Disorders (SCID) and the Schedule for The SCID1 will be administered at baseline to determine study eligibility. The following standard measures will be administered at baseline, both fMRI sessions, and weekly clinic visits:

- The Positive and Negative Affect Schedule is a 20-item questionnaire that measures both positive affect (PA) and negative affect (NA) and is sensitive to subtle changes in affect over time.
- The Hamilton Rating Scale for Depression (HRSD) is a 21-item researcher-rated standardized scale that assesses depressive symptoms and is widely used as a measure of symptom change over time.
- The Inventory of Depression and Anxiety Symptoms (IDAS) is a 64-item self-report questionnaire that comprehensively assesses anxiety and depression symptoms on 10 subscales. The IDAS has excellent psychometric properties and has been validated for assessing reproductive mood disorders.
- The Mood and Anxiety Symptom Questionnaire - Anhedonic Depression Subscale (MASQ-AD) is a 22-item scale that assesses anhedonia (i.e., loss of interest and low positive affect). MASQ-AD scores have been associated with blunted striatal response to reward in previous studies of patients with depression.
- The Greene Climacteric Scale (GCS) is a 21-item scale that is the gold-standard measure of four domains of climacteric symptoms: vasomotor, somatic, anxiety, and depression.
- The Pittsburgh Sleep Quality Index (PSQI) is a 9-item questionnaire that measures the quality and sleep patterns in older adults. \*This measure will only be administered at the two fMRI sessions.

While the SCID and HAM-D are researcher administered, the other measures will be collected through self-report questionnaires using *Qualtrics* or paper and pencil questionnaires.

Despite the use of exclusion criteria designed to reduce risk to participants, depressive symptoms are monitored closely. Any subject who develops severe depressive symptoms (e.g., suicidal ideation) will be discontinued from the study and offered treatment, including inpatient hospitalization.

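### Sections 4.4.1 and 8.5 hold conventional medication back until stopping the protocol has failed, while sections 3.1 and 6 offer treatment at discontinuation; read literally, the withdrawal rule could delay care for a suicidal participant

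*Combined protocol and SAP*

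**What the plan says.** Section 4.4.1 (When and How to Withdraw Subjects) sets out what happens when severe mood symptoms arise on medication. The category covers "Anyone who expresses suicidal thoughts with plans or intent". It also covers a woman who only voices concern about whether she can carry on. Such a participant is discontinued and the protocol is ended for her. The next sentence reads: "Should this step prove to be unsuccessful, conventional medication will be prescribed as needed". Inpatient admission has been arranged for symptoms that cannot be managed otherwise. Section 8.5 (Stopping Rules) repeats this sequence almost word for word.

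The same situation is also covered under Clinical Assessments, in two places. In section 3.1, a subject who develops severe depressive symptoms, with suicidal ideation as the example, "will be discontinued from the study and offered treatment paid for by the study". In section 6 she "will be discontinued from the study and offered treatment, including inpatient hospitalization". Neither place requires stopping to fail first.

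**The concern.** The protocol gives two accounts of when a seriously unwell participant is treated. In one, the offer of treatment comes with discontinuation. In the other, medication follows only after discontinuation has been found not to work. The stricter account sits in the two sections that staff would open when deciding how to withdraw someone, and neither refers to the offer made elsewhere.

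What is at stake is participant safety. A woman with suicidal plans or intent could have medication held while staff wait to see whether stopping hormones helps. No estimate, error rate or power figure is involved.

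**Working it through.** No arithmetic applies. The check is a comparison of the four places and of the facts about who is enrolled.

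| | Sections 4.4.1 and 8.5 | Sections 3.1 and 6 (Clinical Assessments) |
|---|---|---|
| Trigger | Suicidal thoughts with plans or intent, or concern about continuing | Severe depressive symptoms, e.g. suicidal ideation |
| First step | Participation ended | Participation ended |
| Treatment | Medication if the first step fails, and then as needed | Treatment offered together with discontinuation |
| Inpatient care | If symptoms cannot otherwise be managed | Named as part of the offer in section 6; cost covered if it becomes necessary because of the study, in section 3.1 |

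1. *What is the step that may fail?* The sentence immediately before ends the protocol. The earlier three-day repetition of the HRSD suicide item is monitoring, and cannot succeed or fail as a remedy. The dose titration in the following paragraph concerns side effects such as nausea and hypertension. So the step is termination, and medication is conditional on it.

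2. *Whose protocol is ended?* The individual's. Section 8.5 says that it contains no rule for stopping the whole study.

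3. *Does the as-needed wording remove the condition?* No. It governs prescribing once the condition has been met.

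4. *Is there a stated point at which stopping counts as having failed?* No. Section 4.4.2 asks withdrawn women for self-report ratings, and section 8.2 follows the course of an adverse event. Neither sets a time for that judgement.

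5. *Would stopping estradiol be expected to relieve the depression?* Not necessarily in the MDD group. Section 4.1 requires a current MDD diagnosis and describes participants as unmedicated; section 4.2 excludes psychotropic use. The diagnostic interview is at visit 1 (Table 1), and section 6 first gives estradiol at visit 3. The depression therefore predates the drug and is otherwise untreated at entry. This is the main reason not to make medication wait.

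6. *Is there further support?* Some, but it is indirect. Section 1.1 says that "blinded estradiol withdrawal re-precipitates depression in women with a history of perimenopausal depression", and the Summary of Previous Human Experience says that women with such a history "rapidly experience depression recurrence when blindly withdrawn from estradiol". These women were withdrawn after an earlier episode. A woman who becomes severely unwell while on estradiol is in a different situation.

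7. *Does the analysis change?* No. Section 7.3 restricts it to protocol-compliant participants, and section 4.4.2 ends scanning once hormones are discontinued.

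**The case against.** The strongest reply is that the feared case is already covered. The trigger in sections 3.1 and 6 is the broader one on suicidality, so every woman with plans or intent also falls under the offer of treatment there. Admission has been arranged, withdrawal is overseen by the investigators, and no observation period is written down, so a clinician could judge at once that stopping will not be enough. All of this stands. It limits the point to the literal wording of 4.4.1 and 8.5.

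A second reply also stands. The severe-symptom category includes women, controls among them, who only express concern about continuing. For them, stopping first and treating if needed is sensible, so a blanket rule of immediate treatment would be wrong.

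Third, stopping hormones is itself reasonable. Section 1.4 notes that "depression has also been reported to occur with the use of estrogens". Only the wait before medication is in question.

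A reader might infer more than the documents support:

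- *That the protocol denies treatment to discontinued women.* It does not. Nothing in 4.4.1 or 8.5 withdraws the offer in 3.1 and 6, and no section bars prescribing.
- *That the sections contradict each other outright.* They can be read together as a general offer plus an order of steps. Sections 3.1 and 6 also speak of treatment, not medication specifically, and give no explicit timing.
- *That stopping estradiol would worsen her depression.* This would be an inference from women withdrawn in other circumstances, and section 1.1 rests its statement on a manuscript still in preparation.

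The consent wording that section 3.1 introduces on this policy is not in the copy reviewed. It may clarify the offer and is not counted as missing.

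**Conclusion.** The point holds as a minor participant-safety matter. The operative withdrawal rules attach a condition to medication that sections 3.1 and 6 do not, and for a woman with suicidal ideation, plans or intent the literal reading is the worse one. Harm would require staff to follow 4.4.1 or 8.5 without regard to 3.1 and 6.

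Its size cannot be calculated, because the documents give neither a waiting time nor a rate of severe mood symptoms. Few women are likely to be affected, since section 4.2 excludes "current suicidal ideation or psychosis" and past suicide attempts. There is no effect on sample size, power, estimates or error rates.

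The conclusion rests on two readings: that the step which may fail is termination, which the text supports directly, and that the offer in 3.1 and 6 is made at discontinuation, which is the natural but not the only reading.

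**What to change.** In both 4.4.1 and 8.5, replace the two sentences that end the protocol and then make medication depend on the result with:

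> If severe mood symptoms occur, study hormones are stopped for that participant. A participant with suicidal ideation, plans or intent, or other severe depressive symptoms, is offered treatment at discontinuation as in sections 3.1 and 6, including conventional medication as clinically indicated, without first waiting to see whether stopping hormones relieves the symptoms. A participant discontinued only because she is concerned about her ability to continue is offered treatment if symptoms persist or as clinically indicated.

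Keep the admission sentence that follows. Sections 3.1, 6, 7.2 and 7.3 need no change.

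The cost is one amendment submitted to the IRB under section 11. No visit, assessment, CRF field or analysis is added. The downside is that a few women may be offered medication whose symptoms would have resolved on stopping hormones alone.
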